7.7.2.5.2 Expedited Reporting by the Sponsor to a Regulatory Health Authority

Global Safety will monitor data for safety. The Sponsor will manage the expedited reporting of relevant safety information to concerned health authorities, competent authorities, and IRBs/IECs in accordance with local laws and regulations.

7.7.2.5.3 Unblinding Treatment for a Subject During the Trial

To assess an occurrence of a safety observation, Global Safety may unblind the treatment of any subject for whom a safety observation was reported by the investigator to the sponsor as described in [Section 7.7.2.5.1](#).

When the investigator or sub-investigator needs to identify the drug used by a subject and the dosage administered in case of emergency eg, the occurrence of serious adverse experiences, he/she will contact the emergency unblinding call center by telephone and make a request for emergency unblinding. As requested by the investigator or sub-investigator the emergency unblinding call center will provide the information to him/her promptly and report unblinding to the sponsor. The emergency unblinding call-center will make a record promptly however, the investigator or sub-investigator must enter the intensity of the adverse experiences observed, their relation to study drug, the reason thereof, etc., in the medical chart etc., before unblinding is performed.

Additionally, the investigator must go into the IVRS system and perform the unblind in the IVRS system to update drug disposition. In the event that the emergency unblinding call center is not available for a given site in this trial, IVRS/IWRS should be used for emergency unblinding in the event that this is required for subject safety.

In the event that unblinding has occurred, the circumstances around the unblinding (eg, date and reason) must be documented promptly, and the Sponsor Clinical Director notified as soon as possible. Only the principal investigator or delegate and the respective subject's code should be unblinded. Trial site personnel and Sponsor personnel directly associated with the conduct of the trial should not be unblinded.

7.8 Criteria for Early Termination of the Trial

The trial may be terminated early by the eDMC for safety concerns or based on the results of the interim efficacy analysis for futility of the initial 78-week trial (see **Section 8.2.8**).

8.0 STATISTICAL AND ANALYTICAL PLAN

This section outlines the statistical analysis strategy and procedures for the long term safety trial. Changes to analysis plans made after the protocol has been finalized, along with an explanation as to when and why they occurred, will be listed in the Clinical Study Report (CSR) for the trial. Post hoc exploratory analyses will be clearly identified in the CSR. No separate Statistical Analysis Plan (SAP) will be issued for this trial. The statistical analysis of the data obtained from this trial will be the responsibility of the designee from the Clinical Biostatistics Department of the sponsor.

References to either the Screening Visit or the Baseline Visit pertain to the initial 78-week trial. The exact timing of the predose efficacy assessments (screening or baseline) is provided in the Trial Flowchart (**Section 2.2**). Without loss of generality, and within **Section 8** only, a distinction will not be made between the Screening Visit and the Baseline Visit; all predose assessments will be referred to generally as "baseline" assessments. In the event that an assessment was taken at both the Screening Visit and at the Baseline Visit, the data from the Baseline Visit will be used in the analysis.

8.1 Subject Populations to be Analyzed

The analysis populations are the Full Analysis Set population, the Modified Full Analysis Set population and the All-Patients-as-Treated population.

- The Full Analysis Set (FAS) population will serve as the primary population for the analysis of efficacy data in this trial. The FAS population consists of all randomized subjects who have a baseline observation and at least one within-analysis-window (± 6 weeks) post-Randomization observation for the analysis endpoint subsequent to at least one dose of trial treatment. Subjects will be included in the treatment group to which they were randomized. Since the Sponsor's standing internal DMC (siDMC) reviewed unblinded analyses (including the ADAS-Cog) from the first 200 subjects enrolled in the initial 78-week trial, these subjects will be excluded from the FAS population, and hence all efficacy analyses.

All available observations from the initial 78-week trial will be included in the relevant model-based FAS analyses. Observations from the long term safety trial will be included according to the principles outlined above, with the following additional requirement: the subject must have taken at least one dose of study medication within the 28 days preceding Visit 10B and within the 28 days following Visit 10B.

- The Modified Full Analysis Set (MFAS) population will be utilized for sensitivity analyses and is defined identically to the FAS population with one exception: subjects will be required to have either 1) a baseline measurement for the analysis endpoint or 2) at least one within-analysis-window (± 6 weeks) post-dose, post-randomization observation for the analysis endpoint, but not necessarily both.
- The All-Patients-as-Treated (APaT) population will be used for the analysis of safety data in this trial. The APaT population consists of all randomized subjects who received at least one dose of trial treatment, with subjects included in the treatment group corresponding to the trial treatment they actually received. For most subjects this will be the treatment group to which they were randomized. Subjects who take incorrect trial treatment for the entire treatment period will be included in the treatment group corresponding to the trial treatment actually received. Since the siDMC reviewed unblinded analyses from the first 200 subjects enrolled in the initial 78-week trial, these subjects will be excluded from the primary safety analyses.
- For laboratory, vital sign, and ECG endpoints, at least one postdose measurement is required for inclusion in the analysis of each specific parameter, and a Baseline measurement is required for change-from-Baseline analyses (safety only).

8.2 Efficacy Analyses

Details pertaining to the analysis of all endpoints are discussed below. **Table 5** provides a summary of the Primary Endpoints to be analyzed, as well as the analysis approaches that will be used.

The primary analysis approach will include all efficacy observations in the FAS population, including those obtained after the discontinuation of study medication.

Table 5 Analysis Strategy for Primary Endpoints

Endpoint/Variable (Description, Time Point)	Primary vs. Supportive Approach	Statistical Method [†]	Analysis Population	Missing Data Approach
Primary Endpoints				
Primary Endpoints:				
CFB at Week 104 (Visit 13) in ADAS-Cog score	P	Longitudinal ANCOVA	FAS	Model-based
	S	Longitudinal ANCOVA	FAS	Pattern-Mixture Model (Tipping Point)
	S	Longitudinal ANCOVA (Exclude data collected after the introduction of AChEIs and/or study medication discontinuation)	FAS	Model-based
	S	cLDA	MFAS	Model-Based
CFB at Week 104 (Visit 13) in ADCS-ADL score	P	Longitudinal ANCOVA	FAS	Model-based
	S	Longitudinal ANCOVA	FAS	Pattern-Mixture Model (Tipping Point)
	S	Longitudinal ANCOVA (Exclude data collected after the introduction of AChEIs and/or study medication discontinuation)	FAS	Model-based
	S	cLDA	MFAS	Model-Based

The primary model contains categorical terms for treatment, time, geographic region, gender, APOE genotype, study cohort (from initial 78-week trial), and the interaction of time-by-treatment, with the Baseline values of MMSE, and age included as continuous covariates. Terms for the baseline value and the baseline-by-time interaction of the dependent variable will also be included.
 
ADAS-Cog=Alzheimer’s Disease Assessment Scale Cognitive subscale; ADCS-ADL=Alzheimer’s Disease Cooperative Study Activities of Daily Living Inventory; CDR-SB=Clinical Dementia Rating Sum of Boxes; CFB=Change from Baseline; ANCOVA=Analysis of Covariance; cLDA=Constrained Longitudinal Data Analysis; FAS=Full Analysis Set; MMSE=Mini-Mental State Examination; NA=Not Applicable; NPI=Neuropsychiatric Inventory; P=Primary; S=Supportive.
				

8.2.1 Primary Efficacy Analysis

The primary efficacy endpoints are the change from Baseline (CFB) in ADAS-cog score and the change from Baseline in ADCS-ADL score at Week 104 (Visit 13).

A delayed start design will be used to support the potential disease modifying effect of MK-8931 by comparing the 40mg/40mg arm to the Pbo/40mg arm. However, due to increased variance and anticipated dropout rate over time, the study is not powered to demonstrate significance on these endpoints, even if significance was demonstrated at 18 months.

All available data from the initial 78-week trial will be utilized in the analyses, even that from subjects who do not continue into long term safety trial. It is possible that the 40 mg dose may be dropped for reasons due to safety, in which case all subjects would receive 12 mg. The primary comparison in this case would be between the 12 mg / 12 mg arm and the Pbo / 12 mg arm (with any subjects receiving 40 mg or 60 mg excluded from the analysis).

The primary analysis approach will be conducted separately on each of the endpoints.

A longitudinal ANCOVA model will be used on the change scores, with time treated as a categorical variable so as not to impose any restriction on the trajectory of the means over time. The analysis model will adjust for the categorical factors of geographic region (US/Canada, Europe/Australia/New Zealand, Japan, Rest of the World), treatment (one or two remaining dose[s] of MK-8931 or placebo), gender, APOE genotype (APOE 4 positive, APOE 4 negative), baseline use of Vitamin E (0-400 IU/day, > 400 IU/day), baseline AD medication (use of AChEI or memantine, no use of AChEI or memantine), study cohort from the initial 78-week trial (Safety Cohort, Main Cohort) and the interaction of time-by-treatment, with the baseline values of MMSE and age included as continuous covariates. The baseline value of the dependent variable, as well as the baseline-by-time interaction term will also be included. The Week-78 change-from-Baseline mean treatment differences (MK-8931 – placebo), corresponding confidence intervals (CIs), and P-values will be estimated from this model. An unstructured covariance matrix will be used to model the correlation among repeated measurements.

Three supportive analyses will be conducted on each of the Coprimary Endpoints. These analyses will be conducted to assess the effect of 1) missing data using a pattern-mixture model (“tipping-point” analysis), 2) the use of off-regimen data after the subject has permanently discontinued trial medication or after the subject has initiated AChEIs and 3) analyzing the data using the cLDA model on the MFAS population.

For the first sensitivity analyses (tipping-point), the model-based estimates of the mean treatment difference on the change scores, along with the corresponding confidence intervals and p-values will be provided for a range of c values which have been subtracted from the values imputed for the active arms (see 8.2.10) for more details). Of specific interest is the smallest c value that, for a given endpoint, transforms a statistically significant result to a non-statistically significant result.

For the second sensitivity analysis (excluding observations obtained after study medication discontinuation or after the initiation of AChEIs, memantine, or Vitamin E), the model-based estimates of the mean treatment difference on the change scores, along with the corresponding confidence intervals and p-values will be provided.

For the third sensitivity analysis (cLDA model on the MFAS population), the analysis of the primary efficacy endpoints will be conducted using a constrained longitudinal data analysis (cLDA) method proposed by Liang and Zeger [11]. This model assumes a common mean across treatment groups at baseline and a different mean for each treatment at each of the post-baseline time points. The response vector consists of baseline and the values observed at each post-baseline time point. Additional details pertaining to the cLDA model are included in Section 12.5. The model-based estimates of the mean treatment difference on the change scores, along with the corresponding confidence intervals and p-values will be provided as obtained using the cLDA model, with all of the same covariates that were included in the primary model (now excluding the terms for baseline and baseline-by-time interaction). An unstructured covariance model will be used.

Although the baseline measurement is included in the response vector, it is independent of treatment. Hence, the Baseline means are constrained to be the same for different treatment groups. Note that in the event that there are no missing data, the estimated treatment difference from the above cLDA model will be identical to that from a traditional longitudinal analysis of covariance (ANCOVA) model that uses the Baseline value as a covariate. However, unlike longitudinal ANCOVA, the cLDA model accounts for variability in the baseline values, thus providing more accurate standard errors and CIs for individual treatment effects. Additional details pertaining to the use of the cLDA model in this trial are included in [Appendix 4](#).

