5.4 Outcome Measures Rationale

The primary clinical measures in this trial are the Alzheimer's Disease Assessment Scale Cognitive subscale (ADAS-Cog) and the Alzheimer's Disease Cooperative Study Activities of Daily Living Inventory (ADCS-ADL). The ADAS-Cog is a measure of cognition while the ADCS-ADL is a measure of functional ability in activities of daily living. The measures are validated instruments that are acceptable to regulatory agencies, have been used previously in drug trials in this patient population, and can reliably detect clinically relevant changes in AD.

After the initiation of P017, the FDA issued guidance to Sponsors indicating that all trials with BACE1 inhibitors that are longer than two weeks in duration must include routine monitoring of skin. There have been observations in the literature that mice lacking the gene for BACE2 have reduced pigment [30]. In recently completed studies of MK-8931 in two pigmented species (mouse and rabbit), reduced hair pigment was observed within four weeks of treatment in all animals, which was reversible with cessation of treatment. On microscopic examination, normal skin histology was observed except for loss of pigmentation in the hair follicle/shaft. There was no loss of melanocytes. All phases of the hair cycle were present, and no inflammatory or degenerative changes in hair follicles, sebaceous glands, epidermis, or dermis were observed. In contrast to these observations in mouse and rabbit, no change in hair pigment or skin and retinal histology have been observed in monkeys treated for up to 9 months with MK-8931 at exposures 36-fold above those achieved at the highest dose of MK-8931 tested in P017 (60 mg). Furthermore, no adverse events of skin hypo- or depigmentation have been reported thus far in prior human trials of MK-8931.

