5.5 Dose and Administration Rationale

Subjects who tolerated study medication and completed the initial 78-week trial of Protocol 017 may enroll in this long term safety trial. Those subjects who did not complete treatment in the initial 78-week trial, but did continue in the trial and completed the scheduled visits, may be permitted to enroll in this long term safety trial. Subjects who received the 12 mg or 40 mg dose during the initial 78-week trial will continue to receive the same dose in this long term safety trial. They will be referred to as the 12/12 and the 40/40 groups respectively. Subjects who received placebo during the initial 78 week trial will receive the 40 mg dose during this long term safety trial. They will be referred to as the placebo/40 group.

The 40 mg dose has been shown to substantially inhibit CSF A β . The 12 mg dose produces a more moderate reduction in CSF A β and is included since the long term safety of greater inhibition is unknown. Using PK/PD modeling and simulation, 12 mg and 40 mg doses are projected to reduce CSF A β by at least 50% and 75%, respectively, in more than 90% of subjects. It is unknown how much A β lowering is optimal from the perspective of both safety/tolerability as well as efficacy. Subjects who received placebo during the initial 78 week trial will be treated with the 40 mg dose in the long term safety trial to provide additional information about the long term safety of MK-8931 and to estimate the clinical effects of delayed start of this higher dose.

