6.0 TRIAL OBJECTIVES

6.1 Primary Trial Objectives

There are two primary objectives in which the subjects who received 40 mg / 40 mg will be compared to those who received placebo / 40 mg. Similarly, subjects who received 12 mg / 12 mg will be compared to those who received placebo / 40 mg. The two objectives are as follows:

1. To evaluate the safety and tolerability of MK-8931 in the long term treatment of mild to moderate Alzheimer's Disease.
2. To compare the efficacy of MK-8931 administered to subjects for 24 months to that of subjects administered placebo for 18 months followed by MK-8931 for 6 months using endpoints at follows.
 - the change-from-Baseline score in the ADAS-Cog at Week 104 (Visit 13).
 - the change-from-Baseline score in the ADCS-ADL at Week 104 (Visit 13).

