7.4 Treatments

7.4.1 Trial Treatments

7.4.1.1 Treatments Administered

The rationale for selection of doses to be used in this trial is provided in [Section 5.5 – Dose and Administration Rationale](#). There are no specific calculations or evaluations required to be performed in order to administer the proper dose to each subject.

Subjects who received the 12 mg or 40 mg dose during the initial 78-week trial will continue to receive the same dose in this long term safety trial. They will be referred to as the 12/12 and the 40/40 groups respectively. Subjects who received placebo during the initial 78 week trial will receive the 40 mg dose during this long term safety trial. They will be referred to as the placebo/40 group.

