8.3 Safety Analysis

Subjects from all three arms (40 mg / 40 mg, 12 mg / 12 mg, Pbo / 40 mg) will be included in the safety analyses (with any subject treated with MK-8931 60 mg still excluded from the primary analysis). Where applicable, treatment comparisons will be conducted between the 40 mg / 40 mg and Pbo / 40 mg arms, as well as between the 12 mg / 12 mg and Pbo / 40 mg arms.

The broad clinical and laboratory AE categories consisting of the percentage of subjects with any AE, with a drug related AE, with an SAE, with an AE which is both drug-related and serious, or who discontinued because of an AE are considered as Tier 2 endpoints and will be analyzed. Descriptive Safety Endpoints are considered as Tier 3 events and will also be analyzed.

Analyses will be conducted both on the cumulative data including data from the initial 78-week trial as well as this long term safety trial, no analyses will be conducted on the long term safety trial alone.

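### Section 8.2.1's fallback for a dropped 40 mg dose defines its exclusion by dose received rather than by randomized arm, and sets no time limit

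*Combined protocol and SAP*

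**What the plan says.** Section 7.4.1.1 sets the normal course: "Subjects who received placebo during the initial 78 week trial will receive the 40 mg dose during this long term safety trial". A Pbo/12 arm therefore exists only if 40 mg is dropped.

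Section 8.2.1 provides for that event. If 40 mg is dropped for safety, all subjects receive 12 mg, and the primary comparison becomes 12/12 versus Pbo/12, "with any subjects receiving 40 mg or 60 mg excluded from the analysis". The exclusion has no qualifier on when or for how long 40 mg was taken.

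Three other rules bear on it:

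- Section 8.1, on the FAS: "Subjects will be included in the treatment group to which they were randomized".
- Section 8.2.1, same paragraph as the fallback: "All available data from the initial 78-week trial will be utilized in the analyses, even that from subjects who do not continue".
- Section 8.3, on safety: "with any subject treated with MK-8931 60 mg still excluded from the primary analysis".

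On timing, Section 8.2.6 says only that everyone moves to the remaining dose. Section 7.4.1.2 re-assigns subjects from a dropped arm if enrollment has not finished. That condition governs which tablets subjects receive. It is not repeated in 8.2.1 or 8.2.6 as a condition on the analysis. Section 8.0 states that no separate SAP will be issued.

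**The concern.** Rollover is staggered, starting with the first completer of the initial trial. A drop during the extension would therefore find some placebo subjects already on 40 mg, or past Week 104 on it.

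Taken literally, the rule removes those subjects, together with their 78 weeks of placebo data. It keeps placebo subjects who did not continue and removes nobody from the 12/12 arm. The control arm would then be selected on an event after randomization.

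If the rule is confined to the initial-trial arms, no placebo subject is lost, but a late drop creates a different problem. The planned same-dose delayed-start contrast (40/40 versus Pbo/40) gives up its primary status even though its Week 104 data are complete. What replaces it is 12/12 against placebo subjects scored on 40 mg. Section 6.1 already lists that comparison under its proper name: "subjects who received 12 mg / 12 mg will be compared to those who received placebo / 40 mg". It mixes start time with dose, since Section 5.5 projects that 12 mg and 40 mg lower CSF amyloid "by at least 50% and 75%, respectively, in more than 90% of subjects".

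At stake is the Week 104 contrast on ADAS-Cog and ADCS-ADL, which 8.2.1 offers as support for disease modification.

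**Working it through.** **The plan's own figure.** The Synopsis projects 1960 × 0.70 × 0.90 = 1234.8, given as 1235 entering the extension. This reproduces.

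**Per-arm inputs.** Section 8.2.5.2 and Table 7 give 570 randomized per arm, dropout of 30% at Week 78 and 45% at Week 104, and 90% of completers continuing.

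- Present at Week 78: 570 × 0.70 = 399
- Enter the extension: 399 × 0.90 = 359.1
- Never enter: 570 − 359.1 = 210.9 (37%)
- Observed at Week 104: 570 × 0.55 = 313.5

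**Literal reading.** Let f be the share of placebo rollovers that precede the drop. The documents give no value, so a range is shown.

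- Pbo/12 n at Week 104 = 313.5(1 − f)
- SE of the difference relative to an intact placebo arm, Week 104 data only = √{[1 + 1/(1 − f)]/2}
- The same crediting Week 78 data: arm variance proportional to (1 − r²)/n104 + r²/n78, with depleted n104 = 313.5(1 − f) and n78 = 399 − 359.1f. The Week 78 to 104 correlation r is assumed to be 0.9.
- Non-continuers as a share of the analyzed placebo arm = 210.9/(570 − 359.1f)

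| f | Pbo/12 n | SE ratio, Week 104 only | SE ratio, r = 0.9 | Non-continuers |
|---|---|---|---|---|
| 0% | 314 | 1.00 | 1.00 | 37% |
| 25% | 235 | 1.08 | 1.07 | 44% |
| 50% | 157 | 1.22 | 1.20 | 54% |
| 75% | 78 | 1.58 | 1.46 | 70% |
| 100% | 0 | not estimable | not estimable | 100% |

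For example, at f = 50%: 313.5 × 0.5 = 157; √(3/2) = 1.22; 210.9/390.45 = 54%. With r = 0.7 the middle three SE ratios are 1.08, 1.21 and 1.52.

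**Reading limited to the initial-trial arms.** Here the question is which dose placebo subjects were taking at Week 104, which is extension week 26 in the flow chart. Assume even placebo rollover over D = 1, 2 or 3 years (not given), and ignore visit windows and dropout.

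- Last placebo Week 104 visit, in weeks from first entry: 52D + 26 = 78, 130, 182.
- Remainder of the expected maximum of 260 weeks: 182, 130, 78, or 70%, 50%, 30% of the span. These are shares of calendar time, not probabilities of a drop.
- Drop in that remainder: all of the roughly 314 Pbo/12 scores at Week 104 were obtained on 40 mg.
- Drop at week 52: subjects who entered by week 26 were already scored on 40 mg, 26/(52D) = 50%, 25%, 17%. Those entering between weeks 26 and 52 had part exposure, (52 − 26)/(52D) = 50%, 25%, 17%. The rest, 0%, 50%, 67%, had none.

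Power under the fallback is not computed: the plan states neither the Week 104 effect behind Table 7 nor an effect for 12 mg.

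**The case against.** The best defence is that the intent is clear. The parenthesis names 40 mg and 60 mg together, and 60 mg is not an extension dose, so for 60 mg the phrase can only mean an initial-trial arm. Section 8.3 treats 60 mg subjects in the same way. The literal reading contradicts Section 8.1 and the use-all-data sentence, which is itself a reason to reject it. This stands. A reader might infer that the plan means to discard rolled-over placebo subjects, or that the fallback cannot work at all; the documents do not support either inference. The sentence still says receiving rather than randomized to, and settling the intent does not supply a time limit.

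A second defence is the enrollment condition in 7.4.1.2. It is relevant, because without re-assignment there is no Pbo/12 arm. But it limits re-assignment only, and if it refers to extension enrollment, it describes the very period in which some placebo subjects have already taken 40 mg.

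A third is that little depends on this. A drop is described as not planned, 8.2.2 states that there are no formal hypotheses, 7.2 calls the extension endpoints exploratory, and 8.2.1 says the study is not powered for them. Nothing withdraws the 6.1 comparisons, so 40/40 versus Pbo/40 could still be reported after a late drop. Section 8.0 also requires plan changes to be reported with when and why they occurred, and some sponsor staff stay blinded. All of this stands and limits the severity. Choosing between two readings of an unchanged sentence, however, is not clearly a plan change under 8.0.

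**Conclusion.** The point holds at minor severity. The exclusion as worded reaches placebo subjects whom it probably was not meant to reach, and it conflicts with two rules of the same plan. On the probable reading the fallback is still incomplete, because nothing stops a late drop from replacing a complete same-dose contrast with a mixed-dose one labelled Pbo/12.

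The sample size and SE figures are illustrative. They apply only to the literal reading and depend on f; at f = 0 nothing is lost. A reader might take them as an expected loss of precision, but the documents give neither the rollover timing nor the chance of a drop. The calendar figures likewise rest on an assumed rollover period. The planned 40/40 versus Pbo/40 analysis is unaffected if no dose is dropped.

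**What to change.** In 8.2.1, replace the parenthesis with: (excluding subjects randomized to 40 mg or 60 mg in the initial trial; placebo-randomized subjects in the FAS are retained as randomized, including all their initial-trial data).

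Then add:

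- If 40 mg is dropped after Week 104 data collection is complete, 40/40 versus Pbo/40 remains the primary comparison.
- If it is dropped earlier, 40/40 versus Pbo/40 on Week 104 data collected before the drop is reported alongside the fallback. This is needed because a drop shortly before collection ends would still leave most Pbo/12 scores taken on 40 mg.
- The number of placebo subjects who took 40 mg before Week 104, and for how long, is reported.
- A supportive analysis sets to missing the extension observations of placebo subjects who took 40 mg.

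The cost is a few sentences, with no new visits, data or subjects. The supportive analysis will be less precise at Week 104, which is acceptable because it is not the primary fallback.
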